There are four decades of research on the effects of psychopharmacology on hypnotizability suggesting that while hypnotizability is a trait, it can be modified for the duration of the intervention(70). It is hypothesized that inhibitory left DLPFC rTMS (cTBS) will increase hypnotizability. It is expected that there will be a significant change in the pre-rTMS to post-rTMS HIP scores. It is hypothesized that the change in hypnotic depth (pre-rTMS to post-rTMS) achieved will be greater for the active rTMS group over the sham rTMS group given the early pilot work that has already been performed(26). It is expected that there will be a significantly greater mean increase in hypnotizability ratings with active rTMS than with the sham rTMS condition at the $p < 0.05$, level.

Secondary Objective C: *To determine the effect of active, inhibitory rTMS (cTBS) over L-DLPFC on the neural network underlying the conflict regulation system as a reflection of effective modulation of the neural circuitry underlying hypnotizability.*

It has been demonstrated that high hypnotizables recruit the right inferior frontal gyrus (rIFG) during conflict tasks while lows recruit the attentional network(32). Inhibitory rTMS has been demonstrated to not only modulate the hypnosis circuitry, but also change the manner in which the brain attends to stimuli(61).

Hypnosis Scans for Secondary Outcome Measure C: All participants will receive the same identical pre-rTMS Stroop task scan(32). After randomization (to either active DLPFC rTMS or sham rTMS) where one half (n=45) will receive active DLPFC rTMS (cTBS), and one-half sham DLPFC rTMS (cTBS) (n=45)(30), all participants have their post-rTMS Stroop task scan session(32).

fMRI Preprocessing and Analysis: All fMRI data will be preprocessed and analyzed using FSL (FMRIB Software Library, version 5.0) (88) and in the manner described in the Primary Outcome Measure. For group analysis, FMRIB's local analysis of mixed effects will be used within a mask of our a priori ROIs rIFG, DMN nodes, and attentional network nodes, thresholded using family-wise error (FWE) corrected $Z > 2.3$; cluster $p < 0.05$. Average contrast of parameter estimate values will be extracted from our ROIs and Spearman's correlations will be calculated between these values and differences in active versus sham rTMS.

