Secondary Hypothesis C: *Active, inhibitory rTMS (cTBS) over L-DLPFC will modulate the neural network that underlies conflict regulation by producing greater activity in rIFG as well as increases in functional connectivity between the right inferior frontal gyrus (rIFG) and the default mode network (DMN) as compared to sham rTMS (sham cTBS).*

Connectivity between rIFG and DMN will be assessed with BOLD and resting state functional connectivity MRI at the baseline time-point and as well as at the post-rTMS time-point for both rTMS conditions (active and sham)(32). It is expected that the stimulation-induced functional connectivity between these the rIFG and the DMN would be increased compared to change in the connectivity in those receiving sham rTMS. It is hypothesized that inhibitory rTMS (cTBS) to L-DLPFC will result in increased fc between the rIFG and the DMN as well as increased activity in rIFG(32).

Analyses will be restricted to the rIFG and the nodes of the DMN for this Secondary Outcome Measure(32). To determine if rTMS condition during the hypnotic state is specifically associated with change in rIFG and DMN activity and functional connectivity, a mask restricted to rIFG and DMN will be utilized to extract the fMRI activity and connectivity data(32). It is expected that the correlation in active rTMS group over L-DLPFC to be stronger than the correlation obtained in the sham rTMS group. Regression analysis will determine the strength of the relationship between the reductions of fMRI activity between dACC and L-DLPFC during the active versus sham rTMS conditions. Regression analysis will be used to investigate whether greater connectivity will be present between rIFG and DMN for active rTMS versus sham rTMS.

Secondary Objective D: *To determine the effect of active, inhibitory rTMS (cTBS) over L-DLPFC on the neural network underlying the post-hypnotic suggestion Stroop Effect.*

Post-hypnotic suggestion of word-blindness eliminates the Stroop effect in high hypnotizables(119). High hypnotizables demonstrate reduced conflict signaling during the Stroop task after the post-hypnotic suggestion of word-blindness(35).

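### The activity regression for Secondary Outcome C names dACC and L-DLPFC instead of rIFG, and C's scan state, region list and direction are not fixed

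*Combined protocol and SAP*

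**What the plan says.** All of the analysis detail for C is in the combined protocol, Section 9.6.2. The separate SAP covers only the Hypnotic Induction Profile scores and the check of the blind.

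- **Regions.** "Analyses will be restricted to the rIFG and the nodes of the DMN for this Secondary Outcome Measure", and "a mask restricted to rIFG and DMN will be utilized to extract the fMRI activity and connectivity data". The preprocessing paragraph for C, a little earlier, instead sets the group analysis in "a mask of our a priori ROIs rIFG, DMN nodes, and attentional network nodes".
- **Hypothesis.** Section 9.6.2 predicts greater rIFG activity and greater rIFG-DMN connectivity under active stimulation.
- **Activity regression.** The sentence given for activity targets "the relationship between the reductions of fMRI activity between dACC and L-DLPFC during the active versus sham rTMS conditions". No rIFG or DMN term appears in it.
- **Connectivity regression.** The sentence that follows compares rIFG-DMN connectivity between active and sham.
- **Scan state.** The scan paragraph says "All participants will receive the same identical pre-rTMS Stroop task scan". The analysis text says "Connectivity between rIFG and DMN will be assessed with BOLD and resting state functional connectivity MRI at the baseline time-point", and then "To determine if rTMS condition during the hypnotic state is specifically associated with change in rIFG and DMN activity and functional connectivity".
- **General strategy.** Section 9.7 gives conflict-task activity, labelled as Secondary Hypothesis C, the same strategy as the primary outcome: the pre/post contrast compared between arms.

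**The concern.** An analyst who follows the activity sentence under C literally would report on dACC and L-DLPFC, which are the regions of Outcomes A and D. That result would say nothing about rIFG activity, which is half of Hypothesis C, and it would look for a fall where the hypothesis expects a rise.

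The unsettled scan state and region list add a second problem. Rest, Hypnotic Stroop and Non-Hypnotic Stroop are separate acquisitions before and after stimulation (Sections 6.2.2 and 6.2.5), so the competing descriptions of C correspond to data that exist. If the choice among them is made after the data are seen, neither an effect size nor a p-value for C can be taken at face value.

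**Working it through.** The documents give no sample size, power, effect size or alpha specific to C, so there is no figure to reproduce. The check is a comparison of texts.

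1. **Is the activity regression inside C's own restriction?** The restriction and the mask name rIFG and DMN. The regression names dACC and L-DLPFC. Section 2.2 places L-DLPFC in the central executive network and gives medial frontal and posterior cingulate cortex for the DMN, and neither dACC nor L-DLPFC is named in C's mask. The regression falls outside it.

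2. **Where does the sentence come from?** The same wording appears under Secondary Hypothesis A in Section 9.6.2, where the analysis is restricted to dACC and L-DLPFC and the regions fit. Hypothesis D carries it almost unchanged, again with those two regions. Carried-over text is the natural explanation.

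3. **Does the direction fit?** The sentence speaks of reductions. Hypothesis C in Section 9.6.2 predicts greater rIFG activity. It does not fit.

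4. **Is the direction of C itself consistent?**

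| Section | rIFG activity | rIFG-DMN connectivity |
|---|---|---|
| 1.2 and 3 | not stated | increase |
| 9.1 | decrease | decrease |
| 9.6.2 | increase | increase |

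Section 9.1 contradicts the others.

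5. **Which scan state?** For activity, the scan paragraph of 9.6.2 and Section 9.7 agree on the Stroop conflict task. For connectivity, 9.6.2 names resting-state MRI. The hypnosis phrase is attached to both measures and agrees with neither.

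6. **Which regions in the group analysis?** Attentional network nodes are in the preprocessing paragraph for C and absent from the restriction and the extraction mask.

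7. **What is left for C if the faulty sentence is struck out?** Three analyses remain:
   - the rIFG-DMN connectivity regression (9.6.2);
   - the family-wise-error-corrected group analysis in a mask that contains rIFG and DMN nodes (9.6.2);
   - the pre/post active-versus-sham comparison that 9.7 assigns to conflict-task activity, using the linear model Y = α + γZ + ε of Section 9.2.

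Of the two regressions written under C, one is on target and one is not.

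**The case against.** The strongest reply is that the intention is plain. The hypothesis, the restriction and the mask all name rIFG and DMN. Section 9.7 supplies a model for conflict-task activity, and Section 9.2 allows that model to be fitted by regression. The hypnosis phrase is template wording that also appears under A and D. C is not confirmatory: Section 9.2 puts the weight on effect sizes for it, and 9.7 does so for the secondary aims generally. On this view a careful analyst would do the right thing.

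Much of this stands, and it limits the point. It does not remove it. Section 9.7 names neither the rIFG nor a particular Stroop run, so the only region-specific activity regression under C remains the wrong one. An effect size needs a defined region, state and direction as much as a p-value does.

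Two stronger readings are tempting, and the documents do not support them.

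- A reader might infer that C cannot be tested at all. The three analyses in step 7 of the working contradict that.
- A reader might cross three states with two measures, count six candidate tests, and compute a false-positive chance of 1 − 0.95^6 = 0.265. Activity and connectivity are two stated components of C, not alternatives. The text ties activity to the Stroop task and rest to connectivity only. The measures come from the same participants and would be correlated, so independence fails. A familywise error rate is also a poor yardstick for an aim reported mainly by effect size.

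**Conclusion.** The point holds in a limited form. The activity regression for C is wrong as written, in its regions and in its direction, and it gives no information on rIFG activity. C is also inconsistent on scan state, on whether attentional network nodes belong, and on the expected sign in Section 9.1. C keeps an on-target connectivity regression, a group analysis and a general between-arm strategy.

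No numerical size can be attached, because the plan gives no operating figures for C. The primary outcome is not affected. That the sentence was carried over from Outcome A is an inference from the identical wording, but the mismatch does not depend on it. The correction is worth making, because it is specific and cheap and without it the activity half of C is left to the analyst's judgement.

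**What to change.** In the combined protocol:

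- **Activity.** In Section 9.6.2, replace the dACC/L-DLPFC sentence under C with a regression of post-minus-pre change in rIFG activity during the Stroop conflict task on arm. Say which Stroop run is meant. Section 9.7 separates C from the post-hypnotic Stroop analysis of D, which points to the non-hypnotic run.
- **Connectivity.** Keep the rIFG-DMN regression and state one scan state for it. Section 9.6.2 already names rest. Moving it to Stroop runs would be a new choice without support in the text.
- **Hypnosis.** Remove the hypnotic-state wording from C, or label that version exploratory.
- **Regions.** Use one list in the preprocessing paragraph, the restriction and the mask, with attentional network nodes in all three or in none.
- **Direction.** Reconcile Section 9.1 with Sections 1.2, 3 and 9.6.2.

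The cost is wording, with no new data. The SAP, dated January 4, 2024, describes data collection and analysis in the past tense. The correction should therefore carry a date, and any choice of state, region or direction made from here on should be reported as post hoc.

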Connectivity between L-DLPFC and dACC will be assessed with resting state functional connectivity MRI(31, 51) at the baseline time-point and as well as at the post-rTMS time-point for both rTMS conditions (active and sham cTBS). Analyses will be restricted to the dACC and L-DLPFC for this Secondary Outcome Measure. To determine if rTMS condition during the hypnotic state is specifically associated with change in dACC and DLPFC activity and functional connectivity, a mask restricted to dACC and DLPFC will be utilized to extract the fMRI activity and connectivity data. It is expected that the correlation in active rTMS group over L-DLPFC to be stronger than the correlation obtained in the sham rTMS group. Regression analysis will determine the strength of the relationship between the reductions of fMRI activity between dACC and L-DLPFC during the active versus sham rTMS conditions. Regression analysis will be used to investigate whether greater connectivity will be present between L-DLPFC and dACC for active rTMS versus sham rTMS.

Secondary Outcome Measure B: *To determine the effect of active, inhibitory rTMS (cTBS) over L-DLPFC on enhancing hypnotizability (as measured by the Hypnotic Induction Profile-HIP and Stroop Task) and hypnotic intensity (as measured by the Hypnotic Intensity Scale-HIS).*

Augmenting hypnosis with active rTMS may potentially produce an intervention that works better (i.e. deeper hypnotic state) and/or extends to a larger part of the population (makes more of the population hypnotizable)(26).

Hypnosis Related Measures: All participants will receive a baseline Stroop task, HIP, and HIS. After randomization (to either active DLPFC rTMS or sham rTMS) where one half (n=45) will receive active rTMS (cTBS), and one-half sham rTMS (cTBS) (n=45)(30), participant will be placed back in scanner and their HIS will be reassessed. After the post-rTMS scans, all participants will be reassessed with the Stroop task and the HIP.

Analysis of Measures: Changes in HIP, Stroop Effect, and HIS between active DLPFC rTMS and sham rTMS conditions will be compared using ANOVA. It is expected that there will be a significantly greater mean increase in HIP, HIS, and Stroop Effect with active rTMS condition than with the sham rTMS condition at the $p < 0.05$, level.

Secondary Hypothesis B: *Active, inhibitory rTMS over DLPFC will increase hypnotizability and hypnotic intensity as compared to sham rTMS.*

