Hypnosis Scans for Secondary Outcome Measure D: All participants will receive the same identical pre-rTMS post-hypnotic suggestion Stroop task scan(35). After randomization (to either active DLPFC rTMS or sham rTMS) where one half (n=45) will receive active DLPFC rTMS (cTBS), and one-half sham DLPFC rTMS (cTBS) (n=45)(30), all participants have their post-rTMS post-hypnotic suggestion Stroop task scan session(35).

fMRI Preprocessing and Analysis: All fMRI data will be preprocessed and analyzed using FSL (FMRIB Software Library, version 5.0) and in the manner described in the Primary Outcome Measure. For group analysis, FMRIB's local analysis of mixed effects will be used within a mask of our a priori ROIs ACC and DLPFC, thresholded using family-wise error (FWE) corrected $Z > 2.3$; cluster $p < 0.05$. Average contrast of parameter estimate values will be extracted from the ROIs and Spearman's correlations will be calculated between these values and differences in active versus sham rTMS.

Secondary Hypothesis D: Post-hypnotic instruction of word blindness after active, inhibitory rTMS (cTBS) over L-DLPFC will reduce dACC activity during the Stroop task (similar to high hypnotizables) as compared to sham rTMS (sham cTBS).

Activity in dACC will be assessed with fMRI(35) at the baseline time-point and as well as at the post-rTMS time-point for both rTMS conditions (active and sham). Long-lasting (~1 hour) inhibitory rTMS (spaced continuous theta-burst stimulation approach(30)) will be applied to L-DLPFC and expect that the stimulation-induced functional connectivity between these two nodes would be increased as a surrogate of increased hypnotizability and therefore increased post-hypnotic Stroop Effect.

Analyses will be restricted to the dACC and DLPFC for this Secondary Outcome Measure. To determine if rTMS condition during the hypnotic state is specifically associated with change in dACC and DLPFC activity, a mask restricted to dACC and DLPFC will be utilized to extract the fMRI activity. The correlation in active rTMS group over L-DLPFC is expected to be stronger than the correlation obtained in the sham rTMS group. Regression analysis will determine the strength of the relationship between the reductions of fMRI activity between dACC and L-DLPFC with active versus sham rTMS conditions.

Secondary Outcome E: *To determine the effect of active, inhibitory rTMS over DLPFC on modulating the neural network that underlies hypnotic analgesia.*

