9.7 Data Analyses

The Primary Mechanistic Outcome Measure for this study is increased functional connectivity between the L-DLPFC and dACC. The Relevant Clinical Outcome Measure is change in hypnotic analgesia as measured by change in pain thresholds. For secondary aims, the emphasis is on identifying the magnitude of effects (clinical significance, effect size) instead of statistical significance. We will test whether the change in connectivity from baseline to post-treatment is greater in the active rTMS group as compared to the sham group. Following the convention in imaging studies, we will conduct our primary analyses treating the contrast (baseline versus post) as one univariate outcome. We do not expect much variation across our narrowly defined subjects, although some variation is still possible. Given that, we will also analyze the data in the linear mixed effects modeling framework (165, 166) allowing for random intercepts (although this is not customary in imaging studies) as a way of sensitivity analysis. The same analytical strategy will be used to test the effect of rTMS on the DLPFC and dACC activity, which is Secondary

Hypothesis A (previously activity portion of Hypothesis 1a-in grant), activity during conflict task (Secondary Hypothesis C), and during post-hypnotic instruction conflict task (Secondary Hypothesis D).

We are using thermal pain stimuli percept-matched to the individual receiving the intervention. Examining the treatment-effect moderating the role of the pain level is not a primary aim of this project.

Moderator/mediator investigation: We will explore various baseline variables as potential moderators of rTMS effect. For this investigation, we will employ the McArthur approach (167, 168) for moderator analysis. We will also examine potential mediators of rTMS effect using the McArthur approach (167, 168) as well as contemporary causal mediation approaches (169-174), which we believe will provide valuable insights regarding the neuromodulation mechanism for the next phase of investigation.

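### The correlation and regression text for Secondary Hypothesis D (and for the activity part of A) in 9.6.2 addresses dACC/L-DLPFC coupling, not the mean dACC activity that D is about, and is not reconciled with 9.7

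*Combined protocol and SAP*

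**What the plan says.** All references are to the combined protocol and SAP. The separate SAP of January 2024 deals only with HIP scores and the blind, so it does not bear on this point.

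- **Hypothesis D (1.2, 3, 9.1 and 9.6.2).** The word-blindness instruction given after active stimulation "will reduce dACC activity during the Stroop task (similar to high hypnotizables) as compared to sham rTMS (sham cTBS"). This is a between-arm statement about the level of dACC activity.
- **Section 9.6.2, analysis of D.** Four elements appear, with no order of priority:
  - a group map: "For group analysis, FMRIB's local analysis of mixed effects will be used within a mask of our a priori ROIs ACC and DLPFC";
  - a Spearman step relating the extracted ROI values to the active/sham difference;
  - an extraction whose purpose is given as "To determine if rTMS condition during the hypnotic state is specifically associated with change in dACC and DLPFC activity";
  - two closing sentences: "The correlation in active rTMS group over L-DLPFC is expected to be stronger than the correlation obtained in the sham rTMS group" and "Regression analysis will determine the strength of the relationship between the reductions of fMRI activity between dACC and L-DLPFC with active versus sham rTMS conditions".
- **Section 9.6.2, analysis of A.** Near-identical wording is used: "Regression analysis will determine the strength of the relationship between the reductions of fMRI activity between dACC and L-DLPFC during" the active versus sham conditions.
- **Section 9.7.** "The same analytical strategy will be used to test the effect of rTMS on the DLPFC and dACC activity", and the sentence goes on to name Secondary Hypotheses A, C and D. The strategy meant is the primary one: the baseline-to-post contrast is a single outcome compared between arms. Section 9.2 writes the model as Y = α + γZ + ε, with Z = 1 for active.

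**The concern.** The two closing sentences follow directly on the stated aim of relating stimulation condition to change in activity, so they read as the way that aim is met. They cannot meet it. How closely two regions' reductions go together across participants says nothing about whether either region's activity fell.

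For Secondary B and E, 9.6.2 states an ANOVA on change with an expected greater mean change at the 0.05 level. D has no such sentence in 9.6.2. The same dACC/L-DLPFC regression sentence also stands under C, whose regions are the rIFG and the default mode network, which suggests carried-over text.

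Two errors become possible. A difference in coupling without any fall in dACC activity could be reported as support for D. And a real fall could be judged unsupported because the correlations did not differ. Since 9.7 offers another analysis and nothing ranks them, either result could be presented as the test of D.

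**Working it through.** **The plan's own figure.** The only power stated is 0.8 for the primary connectivity outcome (9.2: d = 0.8, 40 usable per arm, two-sided 0.05). The standard two-sample formula does not return it: d·√(n/2) = 0.8 × √20 = 3.58, and Φ(3.58 − 1.96) = 0.947 (0.942 with the t distribution). A power of 0.8 with 40 per arm corresponds to d of about 0.63. That is a separate matter. No power, effect size or correlation is given for D, so the figures below rest on assumptions.

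**Step 1: a shift leaves a correlation unchanged.** Let x and y be one participant's L-DLPFC and dACC change. If every active participant's values move by constants a and b, corr(x + a, y + b) = corr(x, y). The same holds for the slope of y on x. The difference in mean y moves by b.

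**Step 2: closed form for comparing correlations.** Reading the correlation sentence as a comparison of across-participant correlations, z = [atanh(r_active) − atanh(r_sham)] / √(2/(n − 3)). With n = 40 the denominator is √(2/37) = 0.2325.

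- Equal correlations: expected z = 0, so rejection is 5% whatever the mean shift.
- 0.3 to 0.6: (0.693 − 0.310)/0.2325 = 1.65; Φ(1.65 − 1.96) ≈ 0.38.
- 0.2 to 0.6: (0.693 − 0.203)/0.2325 = 2.11; Φ(2.11 − 1.96) ≈ 0.56.

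**Step 3: simulation.** Bivariate normal change scores with unit SD, 40,000 trials per row, two-sided 0.05. Entries are rejection rates at 40 per arm (the usable number in 9.2), with 45 per arm (the number in the D text of 9.6.2) in brackets. Paired correlations are sham/active.

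| Scenario | Correlation comparison | Slope-by-arm interaction | Arm comparison of mean dACC change |
|---|---|---|---|
| dACC falls 0.8 SD; r 0.3/0.3 | 5% (5%) | 5% (5%) | 94% (96%) |
| Both regions fall 0.8 SD; r 0.3/0.3 | 5% (5%) | 5% (5%) | 94% (96%) |
| dACC falls 0.69 SD; r 0.5/0.5 | 5% (5%) | 5% (5%) | 86% (90%) |
| dACC falls 0.8 SD; r 0.3/0.6 | 38% (43%) | 31% (35%) | 94% (96%) |
| No mean difference; r 0.3/0.5 | 18% (20%) | 16% (17%) | 5% (5%) |
| No mean difference; r 0.2/0.6 | 57% (62%) | 49% (53%) | 5% (5%) |
| No mean difference; r 0.3/0.7 | 68% (73%) | 53% (58%) | 5% (5%) |

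The values 0.8 and 0.69 are borrowed from the primary connectivity assumption in 9.2.

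**Step 4: the Spearman step.** In a non-crossover design no participant has an active-minus-sham difference, so as worded the step has no second variable. Reread as the correlation of dACC change with arm, it is a rank comparison of level: it rejects in 93% for a 0.8 SD fall with r 0.3/0.3, and in 4% to 5% with no mean difference (40 per arm, 4,000 trials). Parts of 9.6.2 can therefore be read so as to address D, and parts cannot.

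**The case against.** A reader might infer that the test written for D has about 5% power. The documents do not support that. Section 9.7 names D and assigns it the arm comparison of change, and the model is in 9.2. Section 9.6.2 itself also plans a group analysis of activity and a Spearman step that can be read as a comparison of level. An analyst who reads only 9.6.2 would not necessarily miss a real reduction.

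Three further limits stand:

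- The correlation sentence is an expectation. It has no statistic and no rejection rule, and the Fisher z comparison is one way of making it operational.
- The 5% needs equal correlations in the two arms, while the D text expects connectivity between the two nodes to rise. However, functional connectivity within a person is a different quantity from the across-participant correlation of activity reductions, and a rise in one need not raise the other.
- Correlation could mean each participant's dACC/L-DLPFC connectivity. The tabulated rejection rates for coupling then do not apply, though connectivity is still not activity.

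It can also be said that 9.2 and 9.7 put effect sizes ahead of p-values for secondary aims and that no power is claimed for D. That lowers the stakes for significance testing but does not remove the mismatch: a difference between two correlations is not an effect size for reduced dACC activity. Nor does the group map settle the matter, because the D text specifies no contrast for it and does not rank it against the rest.

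**Conclusion.** The point holds as a mismatch between hypothesis and analysis text, left unreconciled between two sections. In 9.6.2 the closing correlation and regression sentences for D, and the matching ones for the activity part of A, concern coupling and cannot estimate a difference in mean activity. Section 9.7 already contains an analysis that can.

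If the coupling text were used as an across-participant comparison with 40 per arm, it would be blind to a pure mean shift (5%), and it could reject in 57% of trials with no mean difference at correlations of 0.2 versus 0.6. The 9.7 comparison would have about 94% power at d = 0.8 and about 86% at 0.69. All of these rest on assumed effect sizes, assumed correlations and normal change scores.

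This is not a finding that D is underpowered. It affects what may be concluded about D, and it should be corrected because several unranked analyses leave the choice open after the data are seen.

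**What to change.** In 9.6.2:

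1. State that D and the activity part of A are tested by the 9.7 model: pre-to-post change in the mean ROI activity estimate regressed on arm. For D this is the dACC estimate during the post-hypnotic Stroop run. Report the active-minus-sham difference with a 95% confidence interval, which also serves the stated emphasis on effect sizes.
2. Label the stronger-correlation expectation and the regression on the relationship between reductions as exploratory coupling analyses that cannot support a conclusion of reduced activity.
3. For E, keep the ANOVA on change as the test and label the regression on the relationship between reductions in the analgesia network as exploratory.

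The cost is wording only. The ROI values are already to be extracted and the model is already written in 9.2 and 9.7, so no new data or method is needed. The coupling analyses can still be reported, as exploratory results.
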